#### Exclusion criteria for the acromegalic group:

- 1. Established diagnosis of severe kidney or liver dysfunction, malabsorption, multiple myeloma or other diseases associated with reduced bone quality
- 2. Treatment with supraphysiological doses of glucocorticoids or other drugs that impair bone quality
- 3. Diagnosis of rheumatoid arthritis, psoriatic arthritis or other joint diseases unrelated to acromegaly
- 4. Active drug or alcohol abuse
- 5. Pregnancy
- 6. Known allergy/hypersensitivity to local anaesthetics or disinfectant
- 7. Other factors that render the subject unable to participate in the clinical study, based on the judgment of the investigator(s)

The control subjects will be recruited via social media, the aforementioned database and websites, and matched to the acromegalic study population.

#### Inclusion criteria for the control group:

- 1. Age  $\geq 18$  years
- 2. Ability to provide informed consent
- 3. Ability to stand on both legs for  $\geq$ 5 minutes at a time and walk  $\geq$ 6 meters

#### Exclusion criteria for the control group:

- 1. Established diagnosis of severe kidney or liver dysfunction, malabsorption, multiple myeloma, diabetes or other diseases associated with reduced bone quality
- 2. Treatment with supraphysiological doses of glucocorticoids or other drugs that impair bone quality
- 3. Diagnosis of rheumatoid arthritis, psoriatic arthritis or other joint diseases
- 4. Active drug or alcohol abuse
- 5. Pregnancy

Research protocol – Acromegaly: balance, falls and fracture risk

- 6. Known allergy/hypersensitivity to local anaesthetics or disinfectant
- 7. Other factors that render the subject unable to participate in the clinical study, based on the judgment of the investigator(s)

# C. ASSESSMENT OF RESOURCES

This study will be conducted in collaboration with the department of endocrinology of Aalborg University Hospital, wherefrom patients will be recruited and the physical locale for the procedures provided. The department has access to experienced personnel, who are trained in the use of both HR-pQCT and DXA scanners, and the Osteoprobe. Personnel and equipment for biochemical sampling are also accessible.

For assistance with the procedures regarding balance and postural control, we will collaborate with [name] under the group of [name] at Aalborg University, who is experienced in the use of the balance pad and interpretation of the results it yields.

# D. STUDY PROCEDURES

Patients with an established diagnosis of acromegaly will be recruited from December 2022 to March 2025. Patients will be informed of the study during scheduled visits to the pituitary endocrinology outpatient clinic at Aalborg University Hospital by one of two specialists in pituitary endocrinology. Patients will be given information regarding the study, and if interested, they will be provided with a form to fill out with their contact information, so they can be contacted by the investigators or other staff affiliated with the study. Should the patient agree to be contacted via telephone or e-mail, they will be given an instruction regarding their rights as a participant in a scientific study ("Dine rettigheder som forsøgsperson i et sundhedsvidenskabeligt forskningsprojekt") as well as written material specifically pertaining to the study ("Deltagerinformation"). Should the subject be deemed fit for the study, based on the in- and exclusion criteria, contact will be made via phone or e-mail and they will receive further information regarding the study, and offered a personal meeting with one of the investigators, where details of the study procedures will be outlined. The meeting will take place in a dedicated, undisturbed office at the disposition of the Department of Endocrinology, in order to ensure due privacy during the meeting. In advance, the subject will be informed of the opportunity to bring a relative or other representative to the meeting. At the meeting, the participant and any representative will be informed of the 24-hour deliberation period before providing informed consent. No study procedures will be performed until the informed consent form has been signed by both the participant and the investigator.

As mentioned above, healthy controls will be recruited via the aforementioned database, social media and websites such as www.forsoegsperson.dk. Potential participants who contact the principal investigator through these channels will be provided with written material pertaining to the study ("Deltagerinformation") and a description of their legal rights as a participant (*"Dine rettigheder som forsøgsperson i et sundhedsvidenskabeligt forskningsprojekt"*). Should the potential participant meet the inand exclusion criteria, they will be invited to a personal meeting, where details of the study are explained,

having been informed of the opportunity to bring a representative or relative to the meeting in advance. Should they wish to participate, a 24-hour deliberation period will be given prior to obtaining written informed consent.

After providing informed consent, the participants will undergo a series of study procedures. Bone quality will be assessed by way of High-Resolution peripheral Quantitative Computed Tomography (HR-pQCT) images of the distal radius and tibia. Bone material strength index (BMSi) is assessed using an OsteoProbe. In addition to this, postural control will be assessed using a balance board to obtain a surrogate measure of fall risk. Body composition, bone mineral density and vertebral fracture assessment (VFA) will be analyzed via Dual X-ray Absorptiometry (DXA) scans and peripheral muscle strength will be assessed via hand grip strength and knee extension torque measurements, and visual acuity tested with standard methods. Data will be analyzed using relevant statistical analyses and presented as a cross-sectional study.

# HIGH RESOLUTION PERIPHERAL QUANTITATIVE COMPUTED TOMOGRAPHY (HR-PQCT)

HR-pQCT is a 3-dimensional imaging modality that can be applied to bone and joints *in vivo*, in order to non-invasively assess the quantity and quality of trabecular and cortical bone compartments separately. HR-pQCT will be applied to peripheral skeletal sites, namely the distal radius and tibia, where image slices equivalent to 9 mm of bone will be acquired. From this, parameters such as volumetric bone mineral density (vBMD), cortical density, cortical porosity, trabecular density, trabecular thickness, trabecular spacing and others will be calculated using specialized software. In the same scanning session, images of the wrist and ankle joints will be produced and analyzed for features of arthrosis, such as erosions, osteophytosis and others.

The scanner's gantry is relatively narrow and shallow (rear physical stop) only allowing the distal peripheral skeleton to be accommodated. The limb being scanned is immobilized in a carbon fiber shell. A scout view, essentially a two-dimensional x-ray scan, is obtained so that the operator can identify a precise region for the three-dimensional measurement. Because HR-pQCT uses a polychromatic X-ray source it is subject to beam hardening as well as scatter artefacts, which can significantly impact geometric and densitometric measures. Once the images have been acquired, a default patient evaluation protocol is used to analyze the scans over the entire 9 mm three-dimensional region to assess a wide range of standard and optional structural and density parameters.

The effective radiation dose for one HR-pQCT scan at the distal tibia or radius is 0,003 – 0,005 mSv, which is considered a low radiation dose. In comparison, a regular chest X-ray yields a dose of 0,01 – 0,1 mSv and dental X-ray yields 0,005 mSv. The worldwide average effective radiation dose from natural background radiation is 2,4 mSv per year. The average effective radiation dose in Denmark is 3 mSv per year.

Estimated time: 30 min.

# WHOLE BODY DUAL X-RAY ABSORPTIOMETRY (DXA) SCAN AND VERTEBRAL FRACTURE ASSESSMENT

Through DXA scans, we will obtain information regarding body composition, hip and spine bone mineral density, as well as examine any previous vertebral fractures using vertebral fracture assessment (VFA). VFA is a function of DXA scanners which allows for visualization of thoracic and lumbar vertebrae (usually T4-L4) in order to detect vertebral fractures. Vertebral fractures can then be classified as either mild, moderate or severe using the method described by Genant et al.

The effective radiation dose is between 0,001 and 0,01 mSv for one whole body DXA scan, between 0,003 and 0,03 mSv for one hip and lumbar spine DXA scan and 0,003 mSv for one VFA scan. As such, the total effective radiation dose for the DXA scans is between 0,007 and 0,043 mSv.

The whole body DXA scan, hip and lumbar spine DXA scan and VFA scan will be performed consecutively.

#### Estimated time: 50 min.

# MICROINDENTATION, BONE MATERIAL STRENGTH INDEX (BMSI) AND THE OSTEOPROBE®

Using the OsteoProbe®, we will by microindentation measure the bone material strength index (BMSi), an *in vivo* surrogate measure of the fracture resistance of the cortical bone in the tibia. The participant is placed in a supine position with the examined leg rotated slightly outward. After identifying the site of interest, located midway between the medial tibial plateau and the medial malleolus, disinfectant is applied to the skin of the tibia being examined. Finally, under local anesthesia and fully sterile conditions, a test probe is inserted through the skin and onto the midshaft of the tibia, and the fracture resistance of the bone tissue is measured. Without removing the probe from the skin, this process is repeated a minimum of eight (maximally 18) times to provide a sufficient number of measurements. By means of a synthetic polymer calibration phantom, the BMSi is calculated via specialized software provided by the manufacturer. After the procedure, a sterile bandage will be applied to the puncture site and all sharp and/or biohazardous materials will be disposed of in an appropriate manner.

Estimated time: 20 min.

# HAND GRIP STRENGTH (HGS) AND LEG EXTENSION STRENGTH

Hand grip strength will be assessed using a digital hand dynamometer as a measure of peripheral muscle strength. Leg extensor strength will be examined using the peak torque measured by an isometric dynamometer mounted on a fixed chair. 3 attempts will be given for each method, and the maximum value recorded. Research protocol - Acromegaly: balance, falls and fracture risk

Estimated time: 10 min.

#### TIMED UP-AND-GO (TUG)

The TUG test is a functional test frequently used to assess balance in older individuals and is performed by measuring the time it takes for an individual to go from sitting to standing position, walk 3 meters, turn around and return to sitting position. A TUG score of >13,5 seconds is associated with an increased risk of falls.

Estimated time: 10 min.

# STABILOMETRY

Postural control will be assessed by means of a force platform that registers Center of Pressure (CoP) as a measure of postural stability. Measurements are performed under a variety of conditions, including eyes open/closed and on different surfaces. From the CoP measurements, parameters such as CoP range and CoP velocity in both antero-posterior and medial-lateral directions will be calculated using specialized software.

Estimated time: 20 min.

# NERVE CONDUCTION TEST

To fully examine all components of balance, nerve conduction will be tested using a handheld device called NC-stat DPN-Check in order to assess any peripheral neuropathy.

Estimated time: 10 min.

#### VISUAL ACUITY TEST

Visual acuity will be tested using an automated refractometer (KR-800S Auto-kerato-refractometer, Topcon Healthcare, The Netherlands).

Estimated time: 10 min.

Our laboratory has ample experience and know-how regarding the above-mentioned methods and their application in different patient groups.

#### QUESTIONNAIRES

Through questionnaires we will obtain information regarding previous falls and fractures, overall quality of life (Acro-QoL), joint-related symptoms (Western Ontario and McMaster universities osteoarthritis Index, WOMAC), fear of falling (Falls Efficacy Scale International, FES-I) and balance (Berg Balance Scale). Medicine lists will be collected from all participants.

#### BIOCHEMICAL BONE MARKERS AND BLOOD SAMPLES

To assess biochemical markers of bone metabolism, we will measure fasting serum levels of procollagen-1 N-terminal propeptide (P1NP, a marker of bone formation) and cross-linked C telopeptide of type I collagen (CTX, a marker of bone resorption) as well as sclerostin (an inhibitor of bone formation). To assess other hormones with influence on bone quality, we will measure levels of vitamin D and parathyroid hormone (PTH). In total, a volume of approximately 16mL of blood (4x 4mL vials) will be collected from each participant, both acromegalic and controls. For practical reasons, these blood samples are frozen after collection, stored in a research biobank, and analyzed in one session upon all participants' completion of the study procedures. Before analysis, Danish Tissue Utilization Register (Vævsanvendelsesregistret) will be consulted; should the participant be listed herein, the blood sample will not be analyzed. After analysis, any remaining material will be destroyed.

Two extra vials of blood (10mL total) will be extracted and stored in a biobank for future research, to enable analysis of any future bone markers or other biomarkers of interest for this project. An application will be submitted to the Danish Data Protection Agency in this regard. Blood samples will be frozen and stored in an encrypted fashion and in compliance with the Danish Data Protection Act for 15 years after completion of the study, or until their destruction is requested by the participant. Blood samples will be collected from both acromegalic subjects and healthy controls, in order to determine differences in biochemical markers between acromegalic subjects and control subjects. Participants will be asked to sign a separate consent form regarding storage of their biological material (blood sample) in a biobank for future research.

All blood samples are stored in a freezer at -80 degrees Celsius. The freezer is located on the premises of Aalborg University Hospital ([name]) and is only accessible by authorized personnel. Sample vials are marked only with a participant number, and the key to link each participant number to a specific participant will be stored on a secure server only accessible by personnel affiliated with the study.

# **IV: DATA COLLECTION**

Following the participants' informed consent, data regarding age, sex, medicine use and clinical information regarding acromegaly (duration, treatment, comorbidities, disease status and more) will be collected from the participants' Electronic Patient Journal (EPJ). For both groups, anthropometric data such as height and weight will be gathered in relation to the DXA scans. The aforementioned data will be entered in a REDCap database on a secure server owned by the North Denmark Region. The information gathered is both for use in the research project itself and for mandatory quality assurance and monitoring, as per the Committee Act, §3, subsection 3. By providing informed consent, the participants acknowledge that the investigators, sponsors and relevant control authorities may access their Electronic Patient Journal with this intent.

# V: DATA ANALYSIS

#### A. STATISTICAL METHODS

### SAMPLE SIZE CALCULATION

Based on another study using HR-pQCT on acromegalic subjects, using the HR-pQCT-derived parameter "trabecular density", mean values of 180 (SD: 40) and 150 (SD: 40) were found for controls and acromegalic patients, respectively. With a significance level of 5% and using 28 acromegalic subjects and 28 controls, the power of this study will be 80% to demonstrate a difference in trabecular density of 30 units.

# STATISTICAL METHODS

Statistical testing will be performed using STATA® version 17 for Mac (StataCorp LLC, Texas, USA).

Data will be summarized using descriptive statistics such as frequency, percentage, mean and standard deviation. Statistical testing will be applied to compare acromegalic subjects to healthy controls, including t-tests, chi-squared tests and Mann-Whitney U tests, where applicable.

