#### C. OBJECTIVES

Aim:

A. To perform a comprehensive, integrated assessment of balance, bone and joint quality, body composition, muscle strength, fear and risk of falling and fracture risk of acromegalic patients.

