#### **B. STUDY POPULATION**

We plan to include thirty male or female patients with acromegaly and thirty age- (+/- 5 years), BMI- (+/- 5 points), and sex-matched non-acromegalic control subjects.

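### Controls are matched on age, BMI and sex, but no named analysis uses these factors, which costs precision

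*Combined protocol and SAP*

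**What the plan says.** Section III.B plans thirty patients and "thirty age- (+/- 5 years), BMI- (+/- 5 points), and sex-matched non-acromegalic control subjects". After the exclusion criteria for the patient group it adds: "The control subjects will be recruited via social media, the aforementioned database and websites, and matched to the acromegalic study population". Neither sentence says whether each control is tied to one patient (1:1) or the control group as a whole is made similar (group matching).

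Section V.A, Statistical methods, lists descriptive statistics and then: "Statistical testing will be applied to compare acromegalic subjects to healthy controls, including t-tests, chi-squared tests and Mann-Whitney U tests, where applicable". It does not say whether the t-tests are paired. Section III.D adds only: "Data will be analyzed using relevant statistical analyses and presented as a cross-sectional study". No section names a regression, a covariate-adjusted or stratified comparison, or an explicitly paired test.

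The sample size paragraph in V.A states that, "using 28 acromegalic subjects and 28 controls, the power of this study will be 80" per cent for a 30-unit difference in trabecular density, with SD 40 in each group.

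The data that adjustment needs will exist. Section IV collects age and sex, and on body size says: "For both groups, anthropometric data such as height and weight will be gathered in relation to the DXA scans".

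**The concern.** Matching removes large group differences in the chosen factors, but the benefit in precision comes only if the analysis takes the factors into account. A test that ignores them leaves the variation due to age, sex and BMI in the error term, so intervals are wider than they need be. In a rare disease with thirty patients, that precision is hard to recover by recruiting more.

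The limits of 5 years and 5 BMI points also leave room for a mean age or BMI difference between the groups. Such a difference would move the unadjusted estimate up or down, and no named analysis would correct it. Both points hold whether matching is 1:1 or by group.

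**Working it through.** **Inputs from the documents.** SD 40 in each group, difference 30, 5% level, 28 per group in the power statement (V.A); 30 per group and the matching limits (III.B). A two-sided test is assumed because the documents do not state it; a one-sided test would need only 22 per group.

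**Assumptions, not document figures.** Age, sex and BMI together explain a share R² of the outcome variance, in equal parts, with R² between 0.1 and 0.4. Age SD is 14 and BMI SD is 5.

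**1. The plan's own figure.** For two independent groups, SE = 40 × √(2/28) = 10.69. Then 30/10.69 = 2.806, and 2.806 − 1.960 = 0.846, which gives power of 80.1% (78.7% with the t distribution). With 30 per group, SE = 40 × √(2/30) = 10.33 and power is 82.8% (81.5% with t). The stated 80% therefore reproduces as an unmatched two-sample calculation, and matching plays no part in it.

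**2. Precision with adjustment, 30 per group.** If the covariates are balanced, SE = 10.33 × √(1 − R²) on 60 − 2 − 3 = 55 degrees of freedom, and the half-width is 2.004 × SE. The power columns come from simulation (10,000 to 40,000 datasets per setting); repeat runs agree to within about 1 to 1.5 points.

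| R² | Half-width by formula | 1:1 matching: unadjusted → adjusted power | Group matching: adjusted power |
|---|---|---|---|
| 0.1 | 19.6 | 82% → 85% | 84% |
| 0.2 | 18.5 | 83% → 89% | 88% |
| 0.3 | 17.3 | 85% → 93% | 92% |
| 0.4 | 16.0 | 86% → 96% | 95% |

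Under group matching, unadjusted power stays at about 81% to 83% throughout. The unadjusted half-width is about 20.6. Across repeat runs the full ranges are 81–87% unadjusted and 83–96% adjusted. If R² is 0, adjustment loses about 0.2 points (1:1 matching) to at most 2.5 points (group matching).

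**3. False positives.** With 1:1 matching and within-pair correlation r, the unpaired test assumes a variance of 2σ²/n when the true variance is 2σ²(1 − r)/n. Its actual two-sided error is 2Φ(−1.960/√(1 − r)), which is 3.9% at r = 0.1 and 1.9% at r = 0.3. Simulation with no gap gives 3.8% down to 1.4% over the R² range. The unpaired test is therefore conservative.

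**4. Imbalance inside the limits (illustrative).** If each control's BMI falls uniformly within ±5 of its patient's, the mean gap over 30 pairs has SE (10/√12)/√30 = 0.53 points. The assumed slope is 40 × √(R²/3)/5, or 1.46 units per BMI point at R² = 0.1 and 2.92 at R² = 0.4. A chance gap of one SE shifts the difference by 0.53 × 1.46 = 0.8 to 0.53 × 2.92 = 1.5 units, and a 1-point gap shifts it by 1.5 to 2.9 units, against the planned 30. A 2-point gap is 2/0.53 = 3.8 SEs, so it would have to be systematic.

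**5. Skewed outcomes.** Assume a log-normal outcome with group ratio 1.4, R² = 0.2 and 30 per group. At log SD 0.5 and 0.8, power is 79% and 42% for the adjusted model on the log scale, and 69% and 34% for Mann-Whitney U. An untransformed adjusted model with robust (HC3) standard errors reaches 70% and 28%, against 70% and 34% for Mann-Whitney U in the same run. Only the log-scale model improves on the planned test.

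**The case against.** The strongest reply is that the design already handles these factors. With controls matched to patients, the unadjusted mean difference is a sound estimate, the planned power is met and false positives are not inflated. That stands, and it makes this an efficiency point. At R² = 0.1 the gain is only 2 to 3 power points, and the larger gains rest on R² values that the documents do not supply.

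The list of tests is also open-ended, t-tests could include paired ones, and III.D promises relevant analyses. So the plan does not rule out adjustment. It does leave the choice until the data are known. A paired t-test would not remove a mean age or BMI gap, because the mean of the paired differences equals the difference of the means.

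A reader might infer a large bias. Under an assumed 2-point BMI gap, with or without 2 years of age, working against the effect, unadjusted power falls to between 74% and 57%. Working with the effect, the estimate becomes 33 to 38 instead of 30. The documents do not support expecting this: nothing in them suggests that controls will fall on one side of the limits.

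Two caveats on the remedy stand. II.B lists altered body composition among the suggested causes of impaired balance, so BMI may lie partly on the pathway for balance and strength; however, matching on BMI already sets that comparison. And categorical outcomes, such as previous falls and vertebral fractures, would remain unadjusted.

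**Conclusion.** The point holds as a matter of precision and robustness, and is worth fixing because the fix is cheap. Matching on age, BMI and sex enters neither the sample size calculation nor any named analysis. The size of the gain depends on the assumed R² of 0.1 to 0.4, so confidence in it is moderate; the omission itself is plain from the text.

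Two further inferences should be resisted. Ignoring the matching does not make the tests invalid: with no gap, the unpaired test rejects too rarely under 1:1 matching and at about its nominal rate under group matching. Nor is the sample size wrong: 30 per group meets the stated 80%. Any gap scenario is illustrative only.

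**What to change.** **In V.A:**

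- Make the main comparison of trabecular density and the other continuous bone, balance and strength outcomes a linear model on group, adjusted for age, sex and BMI. Report the adjusted difference with its 95% confidence interval.
- For body-composition outcomes, which are part of the aim in II.C ("integrated assessment of balance, bone and joint quality, body composition, muscle strength") and are measured by DXA ("we will obtain information regarding body composition, hip and spine bone mineral density"), adjust for age and sex only, because BMI overlaps with the outcome.
- For clearly skewed outcomes, fit the adjusted model on the log scale where a transformation works, and otherwise keep Mann-Whitney U. Do not substitute an untransformed model with robust standard errors.
- Keep the tests now listed as secondary analyses and for categorical outcomes.

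**In III.B:** state whether matching is 1:1 or by group. If 1:1, record a pair identifier and add a pair random effect or pair-clustered standard errors to the adjusted model.

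**Cost:** SAP wording, plus one database field if matching is 1:1. The model uses three degrees of freedom, which costs about 0.2 to 2.5 power points if the factors are uninformative. Pair-clustered standard errors cost a further 1.4 to 2.8 points. Log-scale outcomes are reported as ratios, not differences. The sample size need not change.
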